2.5 Safety Endpoints

Main safety endpoints will be hypercapnia ($\text{PaCO}_2 > 45 \text{ mmHg}$), acidosis ($\text{pH} < 7.35$), hypotension ($\text{SBP} < 90 \text{ mmHg}$), need for NMBA (neuromuscular blockade agents), need for vasopressors, episodes of $\text{ICP} > 20 \text{ mmHg}$ in neurological patients, need for a tracheostomy, infections.

3. Methods

3.1 Study Design

The aim is to perform a 2-arm, single-center, prospective randomized controlled trial. The duration of the study will be approximately one year, aiming to enroll 12 patients for each arm. An informed consent form will be obtained before randomization.

3.2 Study Population

Eligible patients will be selected from the population admitted to the adult ICU (a 20-beds unit), the post-operative ICU (a 13-beds unit), and the NeuroICU (a 10-beds unit).

3.3 Inclusion and Exclusion Criteria

3.3.1 Criteria for inclusion are:

- Age > 18 yo;
- Negative pregnancy test prior to inclusion in the study;
- The informed consent form needs to be signed and dated by the patient or a relative/legal guardian before of any procedure related to the study; if the patient is initially unable to sign the informed consent form, but later regains the ability to sign it, a new informed consent form will be given to the patient and must be signed and dated;
- Mechanically ventilated in Pressure Support Ventilation, according to the decision to the attending physician;
- A patient with prolonged weaning from the mechanical ventilator will be considered eligible. Prolonged weaning is defined as weaning that is still not terminated 7 days after the first separation attempt from the ventilator (by success or death).

A successful weaning is defined as:

1. For intubated patients: extubation without death or reintubation within 7 days after extubation (whether post-extubation noninvasive ventilation was used or not), or ICU discharge without invasive mechanical ventilation within 7 days, whichever comes first;
2. For tracheostomized patients: spontaneous ventilation through tracheostomy without any mechanical ventilation during 7 consecutive days or ICU discharge with spontaneous breathing, whichever comes first (Béduneau et al. 2017);

- Analgesia provided by continuous infusion of remifentanil lasting five days or more and an intolerance to a dose reduction of 0.025 mcg/kg/min defined as the presence of at least one of the following criteria: RASS ≥ 2 , a respiratory rate ≥ 35 breaths/minute, a $\text{PaCO}_2 < 30$ mmHg,

a heart rate > 120 bpm, a systolic blood pressure value > 160 mmHg or an increase of Visual Analogue Scale for pain assessment of ≥ 2 points.

3.3.2 Criteria for exclusion are:

- Hypersensitivity to the active substance or any of the excipients;
- Hepatic or renal impairment;
- Fever (body temperature ≥ 38 °C) or septic shock, hypothermia (body temperature < 35 °C) or presence of active surface cooling systems;
- Hypoxemic respiratory failure ($P/F < 200$ mmHg);
- Hypercapnic patients with a $PaCO_2 > 45$ mmHg;
- Hemodynamic instability requiring high doses of inotropes or vasopressors;
- Delirium state defined as RASS ≥ 3 and CAM-ICU positive;
- Any condition that may contraindicate the use of remifentanil or TTS-fentanyl;
- Patient admitted for postoperative monitoring after elective surgery;
- Patients with a BMI ≥ 35 ;
- Current enrollment or plan to enroll in any interventional clinical study in which an investigational treatment or approved therapy for investigational use is administered within 30 days or 5 half-lives of the agent, prior to the baseline visit;
- EAdi catheter contraindicated.

4. Study Periods, Visits and Assessments

An overview of the study periods and “visits” is provided below.

4.1 Screening Period

The subject will be evaluated for eligibility for the study based on the inclusion and exclusion criteria. A pregnancy test for females in fertile age and an informed consent will be obtained from the subject or proxy, and/or a third party and signed by the investigator, prior to performing any assessment that is considered to be specifically mandated by the study.

Patients considered eligible for the study will be randomized in two arms. An EAdi Catheter, which is a standard nasogastric tube for enteral nutrition, will be positioned and connected to a mechanical ventilator provided with an EAdi module (Servo-U ventilator, Maquet). EAdi, flow, and Paw waveforms will be acquired from the Servo-U ventilator via a RS232 serial port connected to a laptop with dedicated software (SERVO Tracker SCI, version 1.0, Maquet Critical Care 2017). Baseline data will be collected before randomization.

4.2 Treatment Period

The treatment period starts immediately with the baseline assessments.

In Group 1, in which remifentanil infusion is administered alone, the infusion rate will be increased or decreased according to the study protocol based on PaCO₂ value resulting from the Arterial Blood Gases sample (ABG) collected at each visit.

In Group 2, TTS-fentanyl will be administered with a starting dose of 50 mcg/hr simultaneously with the preexistent remifentanil continue infusion. Remifentanil infusion rate will be increased or decreased based on PaCO₂ value resulting from the Arterial Blood Gases sample (ABG) collected at each visit. After randomization, the TTS-fentanyl dose can be modified every 24 hours according to the study protocol to achieve the desired effect in terms of PaCO₂ value resulting from the Arterial Blood Gases sample (ABG) collected.

A priori we will no exceed 0,2 mcg/kg/min for remifentanil infusion in both arms.

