1.1 Remifentanil

Remifentanil is a selective μ opioid receptor agonist indicated for use during anesthesia and for the provision of analgesia in mechanically ventilated critically patients. Remifentanil has an onset of 1 min and quickly achieves a steady state. Differently, from other opioids, it is metabolized by non-specific blood and tissue esterases into a clinically inactive metabolite, resulting in an elimination half-life of fewer than 10 minutes and not correlated at all with the infusion duration. The unique pharmacological profile of remifentanil has proved particularly advantageous in ICU patients (Muellejans et al. 2004). Muellejans et al. randomly compared remifentanil versus propofol-fentanyl sedation regimen in ICU, showing that remifentanil alone allowed the adequate provision of optimal sedation and rapid extubation without the need for propofol in the majority of patients. Remifentanil was associated with less between-patient variability in the mean percentage of time with optimal sedation than was fentanyl. Using conventional opioids such as fentanyl, however, would require constant patient monitoring to avoid over-sedation caused by drug accumulation, resulting in delayed extubation (Muellejans et al. 2004). An RCT published by Akinci et al. comparing remifentanil to fentanyl infusion in postoperative children confirmed the advantages given by the use of remifentanil, but the authors suggested that the short elimination time of remifentanil may also cause some disadvantages. The elevated heart rates, blood pressures, and the increased sedation scores after cessation of remifentanil probably reflected the short elimination time of remifentanil. Moreover, a higher incidence of pain was noticed after end of the remifentanil infusion and probably this could benefit from long-acting analgesic administration before the cessation (Akinci et al. 2005). 23 RCTs with a total of 1905 patients were included in a recent systematic review and meta-analysis comparing remifentanil infusion with other opioids in mechanically ventilated patients. The results of this meta-analysis suggested that the use of remifentanil was associated with a reduction in the duration of mechanical ventilation when compared with other opioids, specifically with fentanyl infusion, probably related to the pharmacokinetics and pharmacodynamics of remifentanil, its rapid onset and offset. Remifentanil

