1.3 IMP-dose rationale

Different patches delivering different doses of fentanyl are available (12.5 mcg/hr, 25 mcg/hr, 50 mcg/hr, 75 mcg/hr, 100 mcg/hr). Because we had to choose only one, we decided *a priori* to adopt a TTS-fentanyl patch delivering 25/hr of the active principle. The reason for this choice was that it is more practical for us to titrate the dose. The starting dose will be 50 mcg/hr (two patches) and, based on the PaCO₂ values, can be increased or decreased every 24 hours, adding or removing two (50 mcg/hr) or three patches (75 mcg/hr). According to the study protocol, the maximum achievable dose of fentanyl is 300 mcg/hr. Due to the completely new usage that we are proposing for this drug, there is a lack of information in the literature about which is the maximum dose administrable to patients. In the *Summary of Product Characteristics* of TTS-fentanyl is specified

that: *“Some patients may require additional or alternative methods of opioid administration when the TTS-fentanyl dose exceeds 300 mcg/hr”*. The conclusion is that we decided not to exceed 300 mcg/hr of transdermal fentanyl.

Moreover, more considerations need to be done:

- We use TTS-fentanyl to wean the patient from remifentanil, a much more stronger opioid routinely used in Intensive Care Unit (ICU);
- Patients in ICU are strictly monitored 24 hours a day and mechanically ventilated, so the risks for respiratory depression is minimum;
- Remifentanil is traditionally infused at rates that may vary from 0.0125 to 0.25 mcg/kg/min. Using tables available for opioid conversion, we can estimate that 300 mcg/hr of transdermal fentanyl corresponds to 180 mg/day of intravenous (IV) morphine and so 1,80 mg of remifentanil. In a subject of 70 kg, 1,80 mg/day of remifentanil correspond to 0,0178 mcg/kg/min of infusion rate, a very low dose for ICU standards (see APPENDIX 3).

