4.3.1 Visits

Visits will be performed at the baseline and every 4 hours for the first 24 hours, every 6 hours for day 2 and day 3.

At each visit we will record:

- An Arterial Blood Gases (ABG) sample will be collected and ABG parameters recorded (pH, PaCO₂, PaO₂, HCO₃⁻, Lactates, SaO₂);
- Glasgow Coma Scale, RASS (see APPENDIX 1-2), the dosage of remifentanil and TTS-fentanyl;
- Respiratory parameters: Ventilation mode, Pressure Support, Respiratory Rate (RR), Tidal Volume(V_t), peep, FiO₂, EtCO₂, SpO₂; if patient is spontaneously breathing: FiO₂, RR, SpO₂.
- Hemodynamic parameters (Heart Rate, SBP/DBP/MAP, need for vasopressors, inotropes).

A baseline 1-hour recording of EAdi, flow, and Paw waveforms will be performed, as well as after 1, 6, 12, 24 for the first day from the time of randomization and every 24 hours for the following days until the end of the observation period for the primary endpoint. Each recording will last one hour for patients mechanically ventilated, 10 minutes for patients weaned from the mechanical ventilator.

Four different situations are possible:

- For patients connected to the mechanical ventilator in pressure support ventilation (PSV), we will perform an expiratory pause maneuver and an inspiratory pause maneuver (both lasting enough to have 2 or 3 spontaneous breaths) with an interval of one minute between each maneuver. The maneuvers will be performed after 30 and 60 minutes from the start of recording.
- If in the meantime the patient is weaned from the mechanical ventilator and spontaneously breathing through a tracheostomy, we will temporarily reconnect the patient to the mechanical ventilator, in PSV mode, with zero peep (ZEEP), we will perform an expiratory

pause maneuver and an inspiratory pause maneuver (both lasting enough to have 2 or 3 spontaneous breaths) with an interval of one minute between each maneuver. In these weaned patients, the maneuvers will be performed after 5 and 10 minutes from the start of recording that will last only 10 minutes;

- If in the meantime the patient is weaned from the mechanical ventilator, extubated, spontaneously breathing and able to cooperate, the patient will be asked to inspire in a close system connected to a pneumotachograph to estimate P_{aw} . The maneuver will be performed after 5 and 10 minutes from the start of recording that will last only 10 minutes;

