5.4 Reporting of previous/concomitant therapy in the CRF

All previous and study-concomitant therapies taken/administered less than or equal to 24 hours prior to randomization into the study will be recorded in the CRF. All medications administered randomization and up to 24 hours post-study drug discontinuation will also be recorded in the CRF. The generic name, start/end dates and times of administration, route, dose regimen, and indication will be recorded.

- Age > 18 yo
- Pregnancy test (-) if female in fertile age
 - Obtain Informed Consent
- Remifentanil infusion lasting > or = 5 days
 - On Pressure Support Ventilation

[figure not shown]

Fig 1. Screening Period

[figure not shown]
GROUP 1

Remifentanil iv alone

At each visit we will record:

- An Arterial Blood Gases (ABG) sample will be collected
- Glasgow Coma Scale, RASS, the dosage of remifentanil;
- Respiratory parameters: Ventilation mode, Pressure Support, Respiratory Rate, Tidal Volume, peep, FiO_2 , EtCO_2 , SpO_2 ; if spontaneously breathing: FiO_2 , RR, SpO_2
- Haemodynamic parameters

EAdi, flow and Paw waveforms will be recorded 1, 6, 12, 24 hours from the time of randomization for day 1 and every 24 hours for the following days.

Day 1

[figure not shown]
Visits every 4 hours

If $\text{PaCO}_2 > 45 \text{ mmHg}$ $\downarrow 0.025 \text{ mcg/kg/min}$
 If $\text{PaCO}_2 40-45 \text{ mmHg}$ $\downarrow 0.0125 \text{ mcg/kg/min}$
 If $\text{PaCO}_2 35-40 \text{ mmHg}$ $\approx \text{no changes}$
 If $\text{PaCO}_2 30-35 \text{ mmHg}$ $\uparrow 0.0125 \text{ mcg/kg/min}$
 If $\text{PaCO}_2 < 30 \text{ mmHg}$ $\uparrow 0.025 \text{ mcg/kg/min}$

Day 2 and 3

Visits every 6 hours

If $\text{PaCO}_2 > 45 \text{ mmHg}$ $\downarrow 0.025 \text{ mcg/kg/min}$
 If $\text{PaCO}_2 30-45 \text{ mmHg}$ $\downarrow 0.0125 \text{ mcg/kg/min}$
 If $\text{PaCO}_2 < 30 \text{ mmHg}$ $\uparrow 0.0125 \text{ mcg/kg/min}$

GROUP 2

Starts TTS fentanyl 50 mcg/hr and maintain remifentanil iv

[figure not shown]
EVERY 24 HOURS

- If $\text{PaCO}_2 > 45 \text{ mmHg}$ remove TTS-fentanyl 25 mcg/hr
- If $\text{PaCO}_2 35-45 \text{ mmHg}$ don't add or remove tts fentanyl
- If $\text{PaCO}_2 30-35 \text{ mmHg}$ add TTS-fentanyl 50 mcg/hr
- If $\text{PaCO}_2 < 30 \text{ mmHg}$ add TTS-fentanyl 75 mcg/hr

At each visit we will record:

- An Arterial Blood Gases (ABG) sample will be collected
- Glasgow Coma Scale, RASS, the dosage of remifentanil and TTS-fentanyl;

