- Respiratory parameters: Ventilation mode, Pressure Support, Respiratory Rate, Tidal Volume, peep, FiO_2 , EtCO_2 , SpO_2 ; if spontaneously breathing: FiO_2 , RR, SpO_2
- Haemodynamic parameters

4 Hours

Day 1
Visits every 4 hours

- If $\text{PaCO}_2 > 45 \text{ mmHg}$ $\downarrow 0.025 \text{ mcg/kg/min}$
- If $\text{PaCO}_2 40-45 \text{ mmHg}$ $\downarrow 0.0125 \text{ mcg/kg/min}$
- If $\text{PaCO}_2 35-40 \text{ mmHg}$ \approx no changes
- If $\text{PaCO}_2 30-35 \text{ mmHg}$ $\uparrow 0.0125 \text{ mcg/kg/min}$
- If $\text{PaCO}_2 < 30 \text{ mmHg}$ $\uparrow 0.025 \text{ mcg/kg/min}$

Day 2 and 3
Visits every 6 hours

- If $\text{PaCO}_2 > 45 \text{ mmHg}$ $\downarrow 0.025 \text{ mcg/kg/min}$
- If $\text{PaCO}_2 30-45 \text{ mmHg}$ $\downarrow 0.0125 \text{ mcg/kg/min}$
- If $\text{PaCO}_2 < 30 \text{ mmHg}$ $\uparrow 0.0125 \text{ mcg/kg/min}$

EAdi, flow and Paw waveforms will be recorded 1, 6, 12, 24 hours from the time of randomization for day 1 and every 24 hours for the following days.

Figure 3. Treatment Period Group 2

[figure not shown]

Figure 4. Study Design

Screening Period	Verify inclusion/exclusion Criteria, Obtain Pregnancy test and Informed consent
Patient Enrolled	Baseline: ABG sample, respiratory and hemodynamic parameters, GCS, RASS, dosage of remifentanil at inclusion, 1-hour recording of EAdi, flow, and Paw
Treatment period	Randomization (group 1 remifentanil alone, group 2 remifentanil + TTS-fentanyl)
1 hour*	Recording of EAdi, flow, and Paw
4 hours* (Visit 1)	ABG sample, respiratory and hemodynamic parameters, GCS, RASS, dosage of remifentanil and TTS-fentanyl
6 hours*	Recording of EAdi, flow, and Paw
8 hours* (visit 2)	ABG sample, respiratory and hemodynamic parameters, GCS, RASS, dosage of remifentanil and TTS-fentanyl
12 hours* (visit 3)	ABG sample, respiratory and hemodynamic parameters, GCS, RASS, dosage of remifentanil and TTS-fentanyl, Recording of EAdi, flow, and Paw

16 hours* (visit 4)	ABG sample, respiratory and hemodynamic parameters, GCS, RASS, dosage of remifentanil and TTS-fentanyl
20 hours* (visit 5)	ABG sample, respiratory and hemodynamic parameters, GCS, RASS, dosage of remifentanil and TTS-fentanyl
24 hours* (visit 6)	ABG sample, respiratory and hemodynamic parameters, GCS, RASS, dosage of remifentanil and TTS-fentanyl, Recording of EAdi, flow, and Paw
30 hours* (visit 7)	ABG sample, respiratory and hemodynamic parameters, GCS, RASS, dosage of remifentanil and TTS-fentanyl

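### The titration schemes raise opioid at low PaCO₂ without using the pH on the same gas, so in an uncommon patient with metabolic acidosis they can lower pH further (minor safety safeguard)

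*Combined protocol and SAP*

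**What the plan says.** Section 4.2 makes PaCO₂ the titration variable for remifentanil in both groups; for Group 2 it reads "Remifentanil infusion rate will be increased or decreased based on PaCO₂ value resulting from the Arterial Blood Gases sample (ABG) collected at each visit". The treatment schemes give the steps.

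| PaCO₂ (mmHg) | Remifentanil, day 1, both arms (mcg/kg/min) | Remifentanil, days 2–3, both arms (mcg/kg/min) | Patch, Group 2, every 24 h (mcg/hr) |
|---|---|---|---|
| <30 | +0.025 | +0.0125 | +75 |
| 30–35 | +0.0125 | −0.0125 | +50 |
| 35–40 | no change | −0.0125 | no change |
| 40–45 | −0.0125 | −0.0125 | no change |
| >45 | −0.025 | −0.025 | −25 |

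The lowest patch row is an instruction ("add TTS-fentanyl 75 mcg/hr"), whereas the text of section 4.2 only permits a change of patch dose. The days 2–3 rows run at "Visits every 6 hours". Remifentanil is capped at 0.2 mcg/kg/min and the patch at 300 mcg/hr.

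At each visit, section 4.3.1 says "An Arterial Blood Gases (ABG) sample will be collected and ABG parameters recorded"; the listed parameters include pH, bicarbonate and lactate. Section 2.5 begins "Main safety endpoints will be hypercapnia" and next names acidosis, defined as pH below 7.35. Entry under section 3.3.1 requires "an intolerance to a dose reduction of 0.025 mcg/kg/min defined as the presence of at least one of the following criteria". PaCO₂ below 30 is one of those criteria, and no entry criterion limits pH or bicarbonate.

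**The concern.** The schemes read a low PaCO₂ as excess respiratory drive and answer it with more opioid. That fits most patients selected for intolerance of a remifentanil reduction. It does not fit a patient whose sample shows both PaCO₂ below 35 and pH below 7.35. That combination means metabolic acidosis, with the low PaCO₂ acting as compensation. In that patient an opioid increase that reduces ventilation raises PaCO₂ and lowers pH further. The value that would identify the patient is on the sample used for the dosing decision, but no branch reads it.

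A separate dosing conflict sits in the same rules. Section 1.3 describes patch changes, in both directions, as two or three 25 mcg/hr patches. The Group 2 scheme removes 25 mcg/hr, one patch, when PaCO₂ exceeds 45. Staff cannot follow both.

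**Working it through.** **1. Which patients are affected.** The documents give no formula, so I assume Henderson–Hasselbalch with the usual constants and bicarbonate held fixed: pH = 6.1 + log₁₀(HCO₃ / (0.03 × PaCO₂)). Setting pH = 7.35 gives HCO₃ = 0.03 × PaCO₂ × 10^1.25.

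- PaCO₂ 30: 0.03 × 30 × 17.78 = 16.0 mmol/L
- PaCO₂ 35: 0.03 × 35 × 17.78 = 18.7 mmol/L

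A gas with PaCO₂ below 35 therefore shows pH below 7.35 only if bicarbonate is under about 18.7.

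**2. Size of the pH effect.** At fixed bicarbonate, a PaCO₂ rise from 30 to 35 lowers pH by log₁₀(35/30) = 0.067.

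- HCO₃ 15: 7.32 to 7.26
- HCO₃ 13: 7.26 to 7.19

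For contrast, at HCO₃ 24 a rise from 28 to 37.5 takes pH from 7.56 to 7.43, which is harmless.

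**3. How much remifentanil the scheme can add on day 1.** There are six visits (4, 8, 12, 16, 20 and 24 h).

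- PaCO₂ stays 30–35: 6 × 0.0125 = 0.075 mcg/kg/min
- PaCO₂ stays below 30: 6 × 0.025 = 0.15 mcg/kg/min. The 0.2 cap allows this in full only from a starting rate of 0.05 or less (0.2 − 0.15).

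These totals assume that PaCO₂ stays in its band, while step 2 assumes that it rises to 35, where day-1 increases stop. They describe different courses and should not be combined.

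**4. Patch against remifentanil.** Section 1.3 equates 300 mcg/hr of patch with 1.80 mg/day of remifentanil and says "1,80 mg/day of remifentanil correspond to 0,0178 mcg/kg/min of infusion rate" in a 70 kg subject. This reproduces: 1800 / 1440 / 70 = 0.01786. Scaling:

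- 50 mcg/hr: 0.01786 × 50/300 = 0.0030 mcg/kg/min
- 75 mcg/hr: 0.01786 × 75/300 = 0.0045 mcg/kg/min

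Net change at a gas where both drugs are adjusted (mcg/kg/min):

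| PaCO₂ | Day-1 row | Days 2–3 row |
|---|---|---|
| 30–35 | +0.0125 + 0.0030 = +0.0155 | −0.0125 + 0.0030 = −0.0095 |
| <30 | +0.025 + 0.0045 = +0.0295 | +0.0125 + 0.0045 = +0.0170 |

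The 24 h gas is the last day-1 visit and also the first patch decision, so at 30–35 the sign depends on which row is applied. With PaCO₂ sustained at 30–35 over 24 h of days 2–3, four reductions give −0.05 against +0.003 from the patch. No patch is added at 35–45. By the plan's own conversion the patch is small, and the exposure is mainly remifentanil below 35 on day 1 and below 30 afterwards.

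**5. How often the hold would apply.** At PaCO₂ 35, pH is 7.42, 7.46 and 7.49 for HCO₃ 22, 24 and 26. At any PaCO₂ below 35, a hold at pH below 7.35 cannot apply unless HCO₃ is under 18.7.

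**6. Patch removal (separate point).** From the 50 mcg/hr start with PaCO₂ above 45, the scheme leaves 50 − 25 = 25 mcg/hr. Removing two patches as in section 1.3 leaves 50 − 50 = 0.

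**The case against.** The case against giving this much weight is good, and most of it stands.

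- **The exposed group is small.** Section 3.3.2 excludes hepatic or renal impairment, septic shock, and instability needing high-dose vasopressors or inotropes. During treatment, section 5.3 forbids haemofiltration and advises against noradrenaline at or above 0.1 mcg/kg/min. Among 24 patients the number affected could be zero. These limits make the case uncommon; they do not tell staff what to do when it arises.
- **The binary endpoint has already been met.** A patient below 7.35 already counts as an acidosis event. A reader might infer that the schemes create new acidosis events and that a pH hold would prevent them. The point does not extend that far. A low-bicarbonate patient just above 7.35 could be pushed across, but the documents give no CO₂ response from which to judge how often, and a hold at 7.35 would not stop it.
- **Clinicians would intervene.** Patients are monitored around the clock, section 5.2 allows standard care, section 7 lets the investigator withdraw a subject, and remifentanil wears off quickly ("resulting in an elimination half-life of fewer than 10 minutes"). This lowers the risk, but none of it is a dosing rule. The short half-life does not help with the patch, whose full effect section 1.2 puts at 12–24 h.
- **The patch wording is partly permissive.** True of section 4.2; the Group 2 scheme is imperative.

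A reader might also infer that the patch is the main hazard, or that the comparison of arms is biased. By the plan's conversion the patch is the smaller component, and the remifentanil rule is identical in both arms. Neither inference is supported.

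**Conclusion.** The gap is real and its weight is minor. Followed as written, the schemes raise opioid in a patient with low PaCO₂ and pH below 7.35, and this can deepen an acidosis already present. The illustrative size is 0.067 pH units for a PaCO₂ rise from 30 to 35 mmHg, assuming fixed bicarbonate. The frequency of such patients and the PaCO₂ response to each opioid step are not in the documents, so no expected number of harmed patients can be given. That the case is uncommon is itself an inference from the exclusions. This is a safety safeguard only.

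The patch-removal conflict stands on its own. It follows directly from the two texts and changes the dose left on a hypercapnic patient.

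**What to change.** Add to section 4.2 and to both treatment schemes: *No table-ordered increase in remifentanil or TTS-fentanyl is made when the same sample shows pH <7.35; the dose is held pending physician review.* In the safety report, list by arm each hold and each increase made at pH below 7.35.

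Separately, state one patch-removal step, in the same words, in section 1.3 and the Group 2 scheme.

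The cost is one sentence in three places, one listing and one aligned step. No new data are needed, because pH, PaCO₂, bicarbonate, lactate and opioid doses are already recorded at each visit. The downside is that a few held patients stay off the PaCO₂ target and may keep a higher work of breathing, which is the primary measure, or have less analgesia. The listing makes those holds visible.

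### Entry sets no upper limit on the remifentanil rate, yet both arms are capped at 0.2 mcg/kg/min, so an eligible patient above the cap faces an implied cut of up to twice the reduction they qualified by not tolerating

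*Combined protocol and SAP*

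**What the plan says.** **Entry.** Section 3.3.1 requires "Analgesia provided by continuous infusion of remifentanil lasting five days or more and an intolerance to a dose reduction of 0.025 mcg/kg/min", and then lists the signs of intolerance, among them PaCO2 below 30 mmHg and a respiratory rate of 35 or more. The synopsis gives the same criterion, with the reduction written per minute and not per kg per minute; the unit in 3.3.1 is used here. No inclusion or exclusion item refers to the current rate. The nearest exclusion is "Any condition that may contraindicate the use of remifentanil or TTS-fentanyl", which is not a rate limit.

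**Customary rates.** Section 1.3: "Remifentanil is traditionally infused at rates that may vary from 0.0125 to 0.25 mcg/kg/min".

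**Cap and start of treatment.** Section 4.2: "A priori we will no exceed 0,2 mcg/kg/min for remifentanil infusion in both arms". On timing, the same section says: "The treatment period starts immediately with the baseline assessments". For Group 2, "TTS-fentanyl will be administered with a starting dose of 50 mcg/hr simultaneously with the preexistent remifentanil continue infusion".

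**Titration.** The schemes printed after section 5.4 give both groups the same remifentanil steps. On day 1 (visits every 4 hours) the rate rises by 0.0125 mcg/kg/min at PaCO2 30-35 and by 0.025 below 30. On days 2 and 3 (visits every 6 hours) it rises by 0.0125 only below 30, and falls by 0.0125 at 30-45. Group 2 may also add 50 or 75 mcg/hr of patch every 24 hours, up to the 300 mcg/hr maximum in section 1.3. Section 4.4 bars the patch in Group 1.

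Nothing says what happens to a patient who enters above 0.2, or to a patient at 0.2 when the scheme calls for an increase.

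**The concern.** The rules cannot all be followed for a patient who arrives on more than 0.2 mcg/kg/min. The patient was selected because a reduction of 0.025 was not tolerated, and the cap then implies a reduction that may be as large or larger. Group 2 is meant to keep its existing infusion while the patch is started, which is not possible unchanged above the cap. If the cut brings back one of the listed intolerance signs, PaCO2 below 30 mmHg, the day-1 scheme and the cap give opposite instructions.

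Two things are at stake. The first is safety: an unplanned opioid reduction in patients chosen for failing a reduction. The second is the primary endpoint: early work-of-breathing recordings in such patients would partly reflect the forced cut and not the randomised comparison.

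**Working it through.** **Inputs.** Cap 0.2 (section 4.2); top of the customary range 0.25 (1.3); qualifying reduction 0.025 (3.3.1), all in mcg/kg/min. Titration steps come from the schemes after 5.4. Remifentanil half-life is under 10 minutes (1.1), and full patch effect comes 12 to 24 hours after application (1.2). Recordings are at 1, 6, 12, 24, 48 and 72 hours (6.1).

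**1. The plan's own conversion.** Section 1.3 equates 300 mcg/hr of patch with 1.80 mg/day of remifentanil. At 70 kg: 1,800 / (70 × 1,440) = 0.01786 mcg/kg/min. The plan prints 0.0178, so the figure is reproduced apart from truncation. It is used below because it is the only stated link between the two drugs' limits.

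**2. Implied cut and remaining room.** Cut = entry rate − 0.2; room = 0.2 − entry rate.

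| Entry rate | Cut to reach cap | Cut / 0.025 | Room below cap |
|---|---|---|---|
| 0.25 | 0.05 | 2.0 | 0 |
| 0.225 | 0.025 | 1.0 | 0 |
| 0.2125 | 0.0125 | 0.5 | 0 |
| 0.2 | 0 | 0 | 0 |
| 0.1875 | 0 | 0 | 0.0125 |
| 0.175 | 0 | 0 | 0.025 |

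From 0.225 upward the implied cut equals or exceeds the reduction that the patient failed. The columns are the same for both arms.

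**3. Reach into the endpoint.** With a half-life under 10 minutes, the first hour covers more than 60 / 10 = 6 half-lives. A cut at the start would therefore be fully expressed at the 1-hour recording, before the patch has its full effect.

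**4. Extra room in Group 2 at the cap.** The patch changes only every 24 hours. The largest dose in force before 72 hours is 50 + 75 + 75 = 200 mcg/hr.
- Starting patch at 70 kg: 50 / 300 × 0.01786 = 0.0030, or 1.5% of the cap.
- Largest dose before 72 hours: 200 / 300 × 0.01786 = 0.0119, or 6.0% of the cap, just under one 0.0125 step.
- Assuming body weights of 50 to 90 kg, the 200 mcg/hr figure runs from 0.0167 to 0.0093.

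Patches added at 24 hours reach full effect at 36 to 48 hours, and those added at 48 hours only at 60 to 72 hours.

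**5. Where the cap blocks anything.** On day 1 it blocks increases at PaCO2 below 35. On days 2 and 3 it blocks only the 0.0125 step below 30, because at 30-35 the scheme orders a decrease.

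**6. Reaching the cap later.** With PaCO2 persistently below 30, six day-1 visits allow 6 × 0.025 = 0.15. A patient entering at 0.05 could then be at 0.05 + 0.15 = 0.2 by 24 hours. A limit at entry alone does not settle what happens at the cap.

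**The case against.** The best reply is that the cap sentence closes a passage on titration and may be meant only to limit increases, so that nobody is cut. The protocol does not describe an immediate cut, and that part of the argument is an inference. But the sentence carries no such restriction, and a patient left on 0.25 would exceed the stated limit from the first hour. On either reading the text has to say which applies.

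It is also fair that the range in section 1.3 is background to a dose conversion and does not describe the patients to be enrolled, and that a cut affecting both arms is balanced in expectation by randomisation. Both points stand. They limit the concern to safety and noise.

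Some stronger readings are tempting, and the documents do not support them:

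- *That the cap biases the trial towards finding work of breathing no higher with the patch.* The blocked remifentanil step is identical in both arms, and just below 0.2 both can rise by the same remaining amount. Only at the cap does Group 2 alone have further study opioid. That extra opioid is part of the randomised treatment, changes only every 24 hours, and is small by the plan's conversion.
- *That about a fifth of patients are affected.* The ratio 0.05 / (0.25 − 0.0125) = 21% is a share of the width of a range, not of patients. Likewise, one patient being 1/12 = 8.3% of an arm says nothing about how many there will be.
- *That a lower limit at entry is missing.* A patient on 0.0125 cannot be reduced by 0.025, so cannot show the required intolerance and already fails the criterion.

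**Conclusion.** The point holds as an inconsistency between the entry criteria, the customary range, the cap and the titration schemes. For a patient entering between 0.2 and 0.25 mcg/kg/min, the rules taken together imply a cut of up to 0.05, as much as twice the qualifying reduction, and may then order an increase that is forbidden. This rests on two assumptions: that the cap applies from the start of treatment, as section 4.2 suggests without saying so, and that some candidates are on rates above 0.2, which section 1.3 makes plausible but does not quantify.

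The consequence is mainly one of safety, with added noise in the early AUC of a 12-per-arm trial. A systematic difference between arms is possible only among patients at the cap. Its size is uncertain and probably small. The plan should be corrected, but the flaw does not by itself undermine the comparison.

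**What to change.** Reconcile sections 1.3, 3.3.1 (with the synopsis), 4.2 and the titration schemes:

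1. Make eligibility by the remifentanil rate at baseline consistent with whatever cap the sponsor confirms, checked before randomisation.
2. State how a patient at the cap is handled in each arm when the scheme calls for an increase. This is needed even with an entry limit, because patients can reach the cap by titration.
3. Report the baseline rate and the time spent at the cap by arm, so that readers can judge any asymmetry.

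The clinical limits themselves are for the sponsor to set; none is proposed here.

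The cost is a line in 3.3.1 and the synopsis, a sentence or two in 4.2 and the schemes, and one descriptive table. No new data are needed, since Table 1 already records the rate at inclusion and at every visit. The downside is that a few candidates at the top of the dose range may be lost, in a trial that plans 24 patients in 12 months.
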